We hypothesize that, compared to untreated controls, EPO therapy in anemic patients with CKD will raise diastolic blood pressure. The magnitude of the increase in diastolic BP at 12 weeks after treatment will be related to endothelial dysfunction and worsening of endothelial function from baseline to 4 weeks. The factors underlying endothelial dysfunction will be explored by interrogating the nitric oxide pathway (24h urine nitrate and nitrite and plasma ADMA), endothelin activation (plasma endothelin 1 concentration), and changes in the renin angiotensin system (seated plasma aldosterone, renin activity, and 24h urine sodium excretion rate). We will use a randomized controlled trial design with open-label administration of EPO to 80 patients in each group and comparison of the responses over 12 weeks of treatment. The dispensing of EPO will depend on which group the participant is randomized to. The immediate start group will be given EPO at randomization and diastolic BP will be assessed after the first 12 weeks of treatment. While the untreated “waitlisted” controls will be treated with EPO after 12 weeks. We then will examine the diastolic BP after an additional 12 weeks of treatment with EPO. Oral iron will be used in both groups to replete iron deficiency, if necessary given lab work. We will observe the relationship between diastolic BP and endothelial dysfunction using paired testing with each subject’s baseline results serving as their own control. Preliminary data show that our sample size has the ability to detect 5 mmHg change in diastolic BP between groups. For endothelial dysfunction, most studies are powered to detect 1-2% change from baseline.

BACKGROUND

Hypertension is believed to be a common adverse effect of EPO therapy ¹⁻⁶. However, the incidence and severity of EIH is difficult to quantify because underreporting of hypertension is common. Underreporting is likely due to 3 reasons: (i) more aggressive management of hypertension through prescription of antihypertensive drugs, (ii) among dialysis patients, closer attention to dry-weight ^{19,20} and (iii) lack of precise quantification, such as by ABPM ²¹. We have conducted a cross-sectional survey

of hemodialysis patients using 44-hour interdialytic ambulatory BP monitoring to conclusively demonstrate that EPO therapy is indeed an independent determinant of hypertension ²².

Importance of CKD in EPO-induced hypertension

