On the other hand, HIF stabilizers may raise EPO to more physiologic levels, reduce crosstalk with vascular EPO-receptors, and mitigate hypertension. A 2014 study demonstrated in a rodent model that compared to EPO, treatment with HIF-stabilizer molidustat corrected anemia associated with subtotal nephrectomy. However, in contrast to EPO, molidustat reduced systolic BP in a dose-dependent manner⁸². The authors postulate that anti-inflammatory and anti-fibrotic effects of the drug on the kidney may be operative. This study further illustrates that increment in Hgb can be dissociated from an increment in BP. Human data are available but are thus far inadequate to address the question of risk for or protection from incident hypertension with HIF stabilizers ⁸³⁻⁸⁶.

RESEARCH PROTOCOL AND TRIAL DESIGN

Overall trial design and plan

To test the notion that EPO treatment in anemic patients with CKD and stage 1 or less hypertension that is treated or untreated with antihypertensive medications will raise BP, we propose a randomized controlled trial with a “waiting-list design” as shown in **Figure 2**. In this design, half of the patients are treated immediately with EPO and the other half are put on a waiting list for 12 weeks, after which they begin treatment. Ultimately, the waitlisted patients are exposed to the intervention, thus serving as their own controls. The design allows between-group comparison by comparing responses in the parallel groups over 12 weeks and within-group comparison for the waitlist group in the second 12 weeks compared to the first 12 weeks. Titration of the dose of EPO will occur every 4 weeks to manage anemia as detailed below. The effect of EPO on BP will be assessed by change in diastolic ambulatory BP measured over 24 hours at baseline and again at 12 weeks in both groups and at 24 weeks in the waitlisted group. At baseline and every 4 weeks thereafter, we will also evaluate changes in clinic BP and albuminuria. At baseline and 4 weeks after intervention, we will measure endothelial function, and collect blood for biomarkers. The biomarkers we will be analyzing are renin, aldo, ET-1, catecholamine, ADMA, and urine nitrates and nitrites.

Figure 2: Trial design and study process

Visit		1	2-3	4	5	6-7	8	9	10
Measurement		Consent	Baseline	Week 4	Week 8	Week 12	Week 16	Week 20	Week 24
PROC	FMD		x	x		DS	DS		
HTN	24h-ABPM		x			x			DS
	Clinic BP	x	x	x	x	x	DS	DS	DS
Labs	24h-urine		x			x			DS
	Blood labs*	x**	x	x	x	x	DS	DS	DS

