Longitudinal resting images will be acquired before inflation. Blood flow estimated by the pulsed Doppler velocity signal using the outer envelope technique to calculate the velocity time integral will be obtained from a mid-artery sample volume at baseline and upon immediate cuff release to assess hyperemic velocity. Peak hyperemic velocity will be determined from the first complete velocity envelope after cuff release. Higher values of hyperemic velocity represent better microvascular dilatation ⁹³. Longitudinal images of the artery in B mode will be continuously recorded for 3 min after cuff deflation. Images will be recorded digitally using an R-wave gated digitizing interface external to the machine (MIA- LLC, Coralville, IA).

A few minutes after deflation, another image will be acquired to reflect a reestablished baseline. The above procedure is repeated to acquire the images in

deviation of 0.93% and between-subject standard deviation of 1.77%. Thus, the test-retest coefficient of variation was 7.2% in our laboratory.

Biomarker measurements

We may use specimen collected as part of this study for analysis of DNA which may include whole genome sequencing. Plasma endothelin-1 will be measured using validated ELISA kits (R&D systems, Inc., Minneapolis, MN). 24h urinary nitrite and nitrate and total nitrates will be measured using the Greiss reaction using kits from R&D systems, Inc. Renin and aldosterone will be measured using a commercial laboratory (LabCorp, Burlington, NC). Plasma ADMA will be measured using LCMS in our biochemistry core lab. The usual labs such as blood counts, chemistries, urine albumin and Na will be measured in the hospital laboratory. Renin + aldosterone lab testing will require the participants to be resting in seated position for at least 15 minutes prior to blood draw.

STATISTICAL METHODS

Outcome Variables

The outcome variables are as follows:

1. Change from baseline to 12 weeks in diastolic BP in EPO treated patients compared to delayed start controls. In the waitlisted group, we will measure the change from 12 weeks to 24 weeks compared to the change from 0 to 12 weeks.

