2. Change from baseline to 12 weeks in systolic BP in the comparisons above. Between group change in hypertension status from baseline to 12 weeks. Worsening of hypertension at any time point will be defined either as an increase in BP medication or an increase in seated clinic diastolic BP of ≥ 10 mmHg or systolic BP ≥ 20 mmHg. Within-group change in hypertension status from 12w to 24 w will be compared to the control period of 0 to 12w in the delayed start group.
3. The primary outcome variable in this aim is to examine the change in FMD from baseline to 4 weeks in those treated with EPO compared to the waitlisted group. The hypothesis being tested is that EPO will cause impairment in endothelial function. Accordingly, those on EPO will have worsening of FMD.
4. The primary outcome variable in this aim is to examine the predictors of change in FMD from baseline to 4 w in those treated with EPO compared to time controls. Predictors of this change will be baseline values of the following variables: ADMA, urine nitrate and nitrite, renin, aldosterone, and plasma endothelin-1 and change from baseline to 4 w in the above variables. This analysis will answer the question: which of the pathways independently is predictive of endothelial dysfunction?

Sample Size

The primary objective of the study is to assess the change from baseline to 12 weeks in diastolic BP in EPO treated patients compared to controls. In the waitlisted group, we will measure the change from 12 weeks to 24 weeks compared to the change from 0 to 12 weeks. We have measured 24h

ambulatory BP in 183 CKD patients 4 weeks apart. The mean diastolic BP at baseline was 68.3 mmHg and at 4 weeks 68.1 mmHg. The mean difference was 0.14 mmHg and the standard deviation of the difference was 10.3 mmHg. With these assumptions, two-tailed tests and 80% power, the required sample size to detect a between-group difference of 5 mmHg is 68 subjects completing the study in each group. Assuming 85% of those randomized complete the trial, we would need to randomize $68/0.85 = 80$ subjects per group, or 160 subjects in total.

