outcome variable controlling for the group assignment (β_i is significant in [C] and $\tau' < \tau$, which provides evidence for mediation rather than suppression); and (4) the mediated effect is statistically significant. For mediators that satisfy conclusions 1 through 3, the significance of mediation (conclusion 4) will be determined via interval estimation of the mediated effect using the asymptotic variance derivation of Sobel ⁹⁸ since the outcomes are the continuous measures. Additional analyses that look at thresholds of change (binary: worsening of hypertension or not) will utilize bootstrapping methods and logistic regression. The proportion of the effect mediated is calculated as the ratio of the indirect effect to the total effect, or $\alpha\beta/\tau$.

The primary outcome for flow-mediated dilatation is change in FMD from baseline to 4 w in those treated with EPO compared to time controls. Predictors of this change will be baseline values of the following biomarkers: plasma ADMA, urine nitrate and nitrite, and plasma renin, aldosterone, and endothelin-1 and change from baseline to 4 w in the above biomarkers. In addition, the baseline FMD will be an independent variable. This analysis will use regression models similar to the above-listed analyses.

Pre-specified sub-group analyses for BP response

- Effect of age: The effect of age (e.g., 65 or more and <65) will be tested using interaction effects.
- Effect of volume overload: Volume overloaded subjects are more likely to show worsening EIH with EPO therapy. In people with volume overload, renin and aldosterone levels are expected to be low and 24-hour urine Na high. We will dichotomize the baseline levels of these markers and examine the outcome on ambulatory BP using interaction effects.

Safety analysis

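### Urine nitrate/nitrite is specified as a 24-hour measure and its week-4 change is a planned predictor of FMD change, but Figure 2 schedules no 24-hour urine at week 4

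*Combined protocol and SAP*

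**What the plan says.** **What the analysis needs.** Outcome Variables, item 4, lists as predictors of FMD change the baseline values of "ADMA, urine nitrate and nitrite, renin, aldosterone, and plasma endothelin-1 and change from baseline to 4 w in the above variables". The FMD regression paragraph, just before the pre-specified sub-group analyses, repeats the list: "plasma ADMA, urine nitrate and nitrite, and plasma renin, aldosterone, and endothelin-1 and change from baseline to 4 w in the above biomarkers". Baseline FMD is added there as a further independent variable.

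**What the specimen is.** Biomarker measurements states: "24h urinary nitrite and nitrate and total nitrates will be measured". The Hypothesis section agrees, describing the plan as "interrogating the nitric oxide pathway (24h urine nitrate and nitrite and plasma ADMA". No spot-urine method and no creatinine indexing is given for this marker anywhere.

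**When it is collected.** In Figure 2 the 24h-urine row is marked at baseline and week 12 for everyone and at week 24 for delayed start only. The Biomarkers row is marked at baseline and week 4, and at weeks 12 and 16 for delayed start. Overall trial design and plan says: "At baseline and 4 weeks after intervention, we will measure endothelial function, and collect blood for biomarkers". Its next sentence reads: "The biomarkers we will be analyzing are renin, aldo, ET-1, catecholamine, ADMA, and urine nitrates and nitrites". That sentence does not say whether the urine is a 24-hour or a spot specimen.

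**The concern.** The mechanistic aim asks which pathway independently predicts endothelial dysfunction, and it is to be answered by a regression on baseline biomarkers and their changes to week 4. One of those change terms has a named specimen that the schedule does not provide at the visit where it is needed.

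Staff who follow the 24h-urine row will collect nothing usable for this term at week 4. Staff who follow the Biomarkers row may improvise with a spot sample. In the first case the term has no observed values, so the model can be fitted only by leaving it out. In the second, the change score subtracts a 24-hour baseline from a spot value, and the result reflects the switch of specimen as well as any effect of treatment. Either way, a decision nobody planned would shape the comparison between pathways. A 24-hour collection that was not made cannot be recovered later.

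**Working it through.** No figure in the plan decides this point, so the check sets the schedule against the assay and analysis text.

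**Step 1. Read the relevant Figure 2 rows against the column headings** (DS = delayed start only).

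| Row | Baseline | Week 4 | Week 12 | Week 16 | Week 24 |
|---|---|---|---|---|---|
| FMD | all | all | DS | DS | – |
| Biomarkers | all | all | DS | DS | – |
| 24h-urine | all | – | all | – | DS |
| 24h-ABPM | all | – | all | – | DS |
| UACR (x3) | all | all | all | DS | DS |

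At weeks 8 and 20, only UACR among these rows is marked.

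**Step 2. Rule out a damaged table.** The 24h-urine row has the same pattern as the 24h-ABPM row. The design text independently gives the ambulatory timing as baseline, 12 weeks, and 24 weeks in the waitlisted group. The FMD row also matches the text (baseline and 4 weeks). The blank at week 4 is therefore not an extraction fault.

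**Step 3. Match intervals.**
- FMD change available: weeks 0–4 in both groups, and weeks 12–16 in delayed start.
- 24-hour urine change available: weeks 0–12 in both groups, and weeks 12–24 in delayed start.
- Overlap with the interval that the regression needs (0–4): none.

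**Step 4. Count what is affected.** The model names five biomarkers: ADMA, urine nitrate/nitrite, renin, aldosterone and endothelin-1. Each enters as a baseline value and a change, giving 5 + 5 = 10 biomarker terms, plus baseline FMD. The gap touches 1 of the 5 change terms. Of the two nitric-oxide markers (ADMA and urine nitrate/nitrite), it touches the change in one. Still available for that pathway are baseline ADMA, the week-4 change in ADMA, and baseline nitrate/nitrite.

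**Step 5. Look for a rescue elsewhere in the plan.** The imputation text under Accounting for missing data covers ambulatory blood pressure only. Imputation would not help in any case if no week-4 values of the measure are observed. The only urine row marked at week 4 is UACR, and nothing in the plan assigns that urine to the nitrate assay.

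**The case against.** The strongest reply is that a week-4 value is clearly intended. The Biomarkers row is marked at week 4, the design text counts urine nitrates and nitrites among the biomarkers, and the 24h-urine row could be read as serving sodium only. This stands to a degree: it makes the problem an internal contradiction and not a plain omission. It does not settle the matter, because the sentence directly before that biomarker list names only blood, and the assay section gives no specimen other than 24-hour urine.

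Three stronger readings are tempting, and the documents do not support them.

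- A reader might infer that the week-4 value will be missing for all 160 participants. What can be said is that no 24-hour collection is scheduled at that visit. Given the marked Biomarkers row, some urine may in fact be taken for this purpose.
- A reader might infer that the main nitric-oxide predictor is lost. The Hypothesis section lists urine nitrate/nitrite and plasma ADMA together and ranks neither, and the ADMA terms are intact.
- A reader might infer that the delayed-start group's treated period breaks a stated analysis in the same way. Figure 2 does lack a 24-hour urine at week 16, beside that group's on-treatment FMD. But outcome 4 and the FMD regression specify only baseline to week 4, and no model for a 12-to-16-week nitrate/nitrite change is written. That blank is a schedule gap, not a conflict with a stated analysis.

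It is also fair to say that the Hypothesis section presents these pathways as exploratory. That limits the weight of the point but does not remove it.

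**Conclusion.** The concern holds as a contradiction between assay, schedule and analysis. If Figure 2 is followed, the baseline-to-week-4 change in urine nitrate/nitrite cannot be computed from the 24-hour measure that the plan specifies. This affects one of five biomarker change terms and one of two nitric-oxide markers, in the mechanistic regression only. The ADMA terms, baseline nitrate/nitrite, the FMD comparison between groups and the primary diastolic blood pressure analysis are untouched.

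The conclusion rests on two readings: that 24-hour urine means the specimen scheduled in the row of that name, and that the Biomarkers mark at week 4 does not silently add a 24-hour collection. The second is an inference from the blood-only wording. If the investigators intend otherwise, the passages still need to be reconciled. The point should be settled before week-4 visits take place, but it does not threaten the trial's main result.

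**What to change.** Reconcile specimen and schedule so that the same measure is used at both ends of the change.

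**Cheapest route.** Keep aliquots of the UACR urine already scheduled at baseline and week 4, assay nitrate/nitrite in them, index the result to urine creatinine, and use that ratio for the week-4 change. Retain the 24-hour values as baseline and week-12 measures. State which baseline value, ratio or 24-hour, enters the regression beside the change. If a treated-period change is wanted in the delayed-start group, do the same at weeks 12 and 16, where UACR urine is also scheduled. Baseline and week 12 would then have both specimen types, so their agreement can be examined.

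**Cost.** Extra assay runs, a storage instruction, and a sentence each in Biomarker measurements and the FMD regression paragraph. Storage must be arranged explicitly: urine albumin goes to the hospital laboratory, and the plan does not mention retaining that urine for research assays. A spot ratio is noisier than a 24-hour total. Averaging three samples would offset part of that, assuming that x3 in Figure 2 means three samples at week 4 as well; the text spells out three consecutive days only for the baseline value used in stratification.

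**Alternatives.** Adding a 24-hour collection at week 4 (and at week 16 if wanted) keeps the specified measure, at the price of a further full-day collection for each participant. If neither is adopted, drop the week-4 nitrate/nitrite change term in advance and limit the conclusion about nitric-oxide change to ADMA.

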Harms will be assessed by monitoring changes in weight, eGFR, CBC, clinic BP, and ABPM. For more definitive assessments, including hospitalizations, serious adverse events will be properly completed and sent to the VAMC DMC as requested. Safety of continued participation will be assessed at each study visit. The stop-points will be treatment-emergent severe adverse events that precludes further exposure to the drug, such as an allergic drug reaction, initiation of renal replacement therapy, or death. If the study drug is stopped, the subject will be continued to be studied so as to not violate the intention-to-treat principle.

Participants

Inclusion Criteria

- Stage 3 or 4 CKD defined as eGFR <60mL/min/1.73m² for ≥3 months or persistent albuminuria for ≥3 months; (i) urine albumin to creatinine ratio of more than 30 mg/g; (ii) urine protein to creatinine ratio of more than 150 mg/g; or (iii) at least 1+ dipstick positive proteinuria. ⁸⁸
- 24h ABPM <140/90 mmHg at baseline in the presence or absence of antihypertensive treatment.
- Hgb between 8 and 10 g/dL.
- No treatment with ESA within the previous 3 months.
- Adults, age 18 and older.

Exclusion Criteria

- Need for packed RBC transfusion in the previous 2 months.
- Myocardial infarction, stroke, or hospitalization for heart failure in the past 2 months.
- In the assessment of the investigator, have hematologic, inflammatory, infectious, or other conditions that might interfere with the erythropoietic response.

Retention of Participants

For half of the participants, only 7 visits are needed. For the others, at least 11 visits over 24 weeks of the trial are needed. We will offer \$20 per visit for participation in the trial to offset travel and time costs.

METHODS

Method of Randomization

Participants will be randomized in a 1:1 ratio to either early or delayed treatment (“waitlisted group”) with EPO according to UACR strata. A random permuted block design will be used to avoid imbalance in assignment to the treatment groups over time. A randomization sequence will be generated by the statistician and individually concealed in sequentially numbered opaque envelopes. After confirming eligibility with the principal investigator, the study pharmacist will dispense EPO according to the randomization sequence.

Measurement of clinic BP

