The standard deviation of the difference in systolic BP is 16.7 mmHg and we can detect an 8.4 mmHg between-group difference using the above assumption. The assessment of endothelial function is another major goal of this application. Position papers on FMD studies 90 state the following: "Typically, significant improvement in FMD can be seen with 20 to 30 patients in a crossover design study and 40 to 60 patients in a parallel-group design study. In studies of this size, the minimal statistically significant improvement that can be detected with intervention is an absolute change in FMD of 1.5% to 2%." The SD of absolute change within subjects in our lab is 0.93%. The sample size proposed (160) will allow us to detect a change of as little as 0.45%. Notably, this change is much more sensitive—approximately one quarter of what is commonly seen with typical sample sizes in conventional FMD studies.

Analysis

The analyses will begin with descriptive statistics. Overall and by-group descriptive statistics will be calculated and examined graphically. Tests for differences in demographics between the early and delayed start groups and characteristics of dropouts will be computed using t-tests, chi square (or Fisher's exact tests if $n < 6$ per cell) to understand if potential differences exist, although such differences are not expected. Comparison of the three UACR strata will be done to assess if there are differences in the populations recruited. Randomization will be within UACR group so that these differences should not bias the trial.

Primary Analysis

To test the hypothesis that early start EPO will worsen the 24-hour DBP assessed by change from baseline to 12 weeks, a mixed model will be used to analyze the results.

We will fit two separate models:

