- model 1: The outcome variable will be 24h ambulatory diastolic BP. The predictors will be indicator variables for group (early or late start), time (baseline and 12 weeks), stratum (UACR: none, high, very high) and all interactions. The random component of the mixed model will include subject and time. Unstructured covariance will be used with estimation of marginal means by maximum likelihood. We expect the interaction between group by time to be significant. The random coefficient analysis does not require baseline systolic BP as a covariate. If the 3-way interaction term (group x time x stratum) is significant, then results will be reported within each stratum. Confirmatory analyses will utilize change from baseline in clinic diastolic BP.
- model 2: The outcome variable will be 24h ambulatory diastolic BP. The predictors will be indicator variables for period within the delayed start group (early or late), time (baseline and 12 weeks from start of period), stratum (UACR: none, high, very high) and

all their interactions. The random component of the mixed model will include subject and time. We expect the interaction between period by time to be significant. If the 3-way interaction term is significant, then results will be reported within each stratum.

Accounting for missing data

Ambulatory BP recording, the gold-standard to assess BP, is carried out only twice during the trial in the parallel group analysis, but clinic BP measurements occur every 4 weeks. Patients who drop out but have some post-baseline measurements of clinic BP will be included in the analyses, thus minimizing loss to follow up. We will impute ambulatory BP as follows: we will use the complete data to build a model that relates the follow-up mean 24-hour ambulatory diastolic BP from the baseline 24-hour ambulatory diastolic BP and the clinic measures using repeated measures Mixed Model regression - then use the expected value from the model for the missing value - and use PROC MI (which generates maybe 5 replicate values to insert variability into the imputation) so that there is a price to pay for imputing.

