Comparison of the cohort with these measurements will also be done to understand if the inferences based on the ambulatory BPs accurately reflect the differences between the treatment groups using the clinic BPs. Repeated measures mixed models (PROC MIXED in SAS) will be utilized to assess the overall differences between the treatment groups using the clinic BPs. Additional analyses will explore the nocturnal patterns between the groups in the ambulatory BPs as well as the pattern over time using circadian models of BP in each group.

Between-group changes in hypertension status from baseline to 12 weeks will be tested using logistic regression. Worsening of hypertension at any time point will be defined either as an increase in BP medication or an increase in seated clinic diastolic BP of ≥ 10 mmHg or systolic BP ≥ 20 mmHg. The McNemar test will be used to compare within-group change in hypertension status from 12w to 24 w to that in the control period of 0 to 12w.

To test the hypothesis that EPO is causal to EIH via worsening of FMD, we will evaluate changes from baseline in FMD. That is, we will test if the worsening is a mediation effect using the technique described by Judd and Kenny⁹⁶ and elaborated by MacKinnon⁹⁷. The technique, expanded here for more than one potential mediator employs three regression equations:

- A. $Y = \beta_0 + \tau X_p + \varepsilon$
- B. $X_i = \beta_0 + \alpha_i X_p + \varepsilon$
- C. $Y = \beta_0 + \tau' X_p + \beta_1 X_1 + \dots + \beta_i X_i + \dots + \beta_k X_k + \varepsilon$ for all mediators together,
or $Y = \beta_0 + \tau' X_p + \beta_i X_i \varepsilon$ for each mediator separately

Y is the outcome result (e.g., change in 24-hour diastolic systolic BP), X_p is the group (early vs delayed start) and X_i represent the k purported mediators. The total effect of the treatment on the outcome (measured by the coefficient, τ) is the sum of direct effect (τ') of the treatment and the mediated, or indirect, effects ($\alpha_i \beta_i$). Mediation is established when four conclusions are met: (1) the treatment predicts the outcome variable (supported by a test of statistical significance of τ in equation [A]); (2) the treatment causes the potential mediator (α_i is significant in [B]); (3) the mediator causes the

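### Worsening of hypertension counts a single unconfirmed clinic rise against an undefined baseline: about 20% of unchanged patients flagged at one visit and about 40% over three, if clinic BP varies as the ambulatory figures do

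*Combined protocol and SAP*

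**What the plan says.** Outcome Variables, item 2, and the hypertension-status paragraph under Accounting for missing data give the same two-part definition. The first part concerns treatment: "Worsening of hypertension at any time point will be defined either as an increase in BP medication". The second part, which is enough without the first, rests on the clinic reading alone and is worded as "increase in seated clinic diastolic BP of ≥ 10 mmHg or systolic BP ≥ 20 mmHg". The test is stated as follows: "Between-group changes in hypertension status from baseline to 12 weeks will be tested using logistic regression". A McNemar test compares the two periods within the delayed-start group.

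Accounting for missing data notes that "clinic BP measurements occur every 4 weeks", so there are three post-baseline visits by week 12. Under Measurement of clinic BP, a visit value is the mean of three readings on one occasion. Figure 2 schedules clinic BP at consent (visit 1) and at baseline (visits 2-3). The definition does not say which of these is the reference, or whether they are averaged.

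The only SDs of change are in Sample Size. For diastolic BP the "deviation of the difference was 10.3 mmHg", from 24h ambulatory recordings in 183 CKD patients 4 weeks apart (mean difference 0.14 mmHg). For systolic BP: "The standard deviation of the difference in systolic BP is 16.7 mmHg". No clinic SD and no expected event rate are given.

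**The concern.** The two cut-offs are close to one SD of the only change variability the plan reports: 10/10.3 = 0.97 SD diastolic and 20/16.7 = 1.20 SD systolic. Either suffices, one visit is enough, and the any-time-point wording can be read as allowing three chances. All the changes share one baseline, so a chance low baseline raises every later comparison.

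The Background says that the incidence of EPO-induced hypertension is hard to quantify. If a large share of events are chance rises, the reported incidence overstates true worsening in both arms and the odds ratio is pulled toward 1. The McNemar comparison is diluted in the same way.

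**Working it through.** **The plan's own figure.** With a difference of 5 mmHg, SD 10.3, 80% power and two-sided 5% (alpha is not stated; assumed), n = 2 × (1.960 + 0.842)² × 10.3² / 5² = 66.6 per group. The t-test version gives 67.6, so 68, and 68/0.85 = 80. The plan's figure reproduces.

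**Assumptions for the worsening rule.** Only the SDs come from the plan.
- Clinic SD of change equals 10.3 (diastolic) and 16.7 (systolic), and none of it is true change.
- Visit errors are independent and normal, with SD 10.3/√2 and 16.7/√2. Changes at different visits then correlate 0.5 through the shared baseline.
- The diastolic–systolic error correlation is 0.65.

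**One visit, no true change.**
- Diastolic: 1 − Φ(10/10.3) = 16.6%.
- Systolic: 1 − Φ(20/16.7) = 11.6%.
- Either, by simulation (400,000 patients): 22%. The range is 20–23% for diastolic–systolic correlation 0.8 to 0.5.

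**Any of weeks 4, 8 and 12, no true change.** Either criterion: 42% (39–44% over the same correlations). Sensitivity:
- SDs 0.7 to 1.2 times as large: 23–50%.
- 30% of the change variance made persistent drift: 38%.
- Changes at different visits correlated 0.7 to 0.9: 30–39%.

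**With a true effect.** I added 5/8 mmHg (diastolic/systolic), either constant from week 4 or gradual (one third, two thirds, then all of it at weeks 4, 8 and 12), with 68 per arm. Power uses the two-proportion normal approximation. For the gradual effect under the literal any-visit rule, rates are 41.9% vs 58.0%:

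z = (0.161 × √68 − 1.96 × √(2 × 0.4995 × 0.5005)) / √(0.419 × 0.581 + 0.580 × 0.420) = (1.328 − 1.386)/0.698 = −0.08, so power is 47%.

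The odds ratio is 1.9. On these figures 42/58 = 72% of the EPO-arm rate would have occurred without any effect.

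| Rule (BP component only) | Gradual: rates, OR, power | Constant: power |
|---|---|---|
| Any visit, single baseline | 42% vs 58%, 1.9, 47% | 76% |
| Any visit, baseline averaged over two visits | 37% vs 57%, 2.2, 62% | 90% |
| Mean of weeks 8 and 12, averaged baseline | 11% vs 26%, 2.9, 63% | 80% |

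Averaging follow-up as well adds nothing for the gradual effect (62% to 63%) and loses 10 points for the constant one (90% to 80%). With SDs 0.7 times as large it loses more: about 86% to 69% (gradual) and 99% to 86% (constant).

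**Medication component.** Study Intervention and Stop points call for more antihypertensive medication after a clinic rise above 20/10 mmHg, and a medication increase is itself an event. I let one visit trigger this when either limit is exceeded against a single baseline reading, with no BP fall afterwards. Any-visit power with the averaged baseline is then 55% (gradual) and 85% (constant), still above 47% and 76%. In that setting the composite's no-effect rate does not fall, because the single-baseline escalations still count.

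**The case against.** **The SDs are ambulatory.** Clinic BP is a different measurement: three seated readings after 5 minutes' rest with no observer in the room. A reader might infer that the plan's own data show 40% of unchanged patients being misclassified. They do not; the figure is conditional on borrowed SDs. This stands, and is why the range is given. Even at 0.7 times those SDs, about 23% are flagged over three visits.

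**The 40% depends on one reading.** The any-time-point phrase may only define status at a given visit, with week 12 tested. The rate is then about 22%. This stands; the text does not settle it.

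**Noise is the same in both arms.** A reader might infer a biased test or an uninformative outcome. Neither follows. Chance rises create no false difference between the groups, and an odds ratio of 1.9 is diluted, not empty. The primary outcome is continuous 24h ambulatory diastolic BP, and clinic BP is also analysed as a continuous measure.

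**Confirmation is not a free cure.** A reader might infer that requiring a sustained rise cuts the false rate to 11%. That is the BP component alone. Single-visit escalation still brings chance rises in through the medication component, and averaging or confirming follow-up gives up power in several settings. This stands, so it is not proposed as the main rule.

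**Two baselines.** Using different baselines between and within groups means that one delayed-start patient could be classed differently for weeks 0–12 in the two analyses. This stands and has to be disclosed.

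**Conclusion.** The point holds in a limited form. The rule needs no confirmation and names no baseline. If clinic change is as variable as the ambulatory change, about 20% of unchanged patients are flagged at one visit and about 40% at any of three (23–50% with SDs 0.7 to 1.2 times as large). These figures also assume independent normal visit errors and a diastolic–systolic correlation near 0.65.

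The consequence is an inflated incidence and a diluted odds ratio for a secondary outcome, not a false treatment effect. Averaging the pre-randomisation readings raised power in every setting run. The gain is smaller when single-visit escalation also produces events, and it then does not clean up the composite incidence; hence the need to show the components separately.

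**What to change.** In Outcome Variables, item 2, and in the hypertension-status paragraph:

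1. For the between-group analysis, define baseline clinic BP as the mean of all scheduled pre-randomisation clinic visits (visit 1 and visits 2-3).
2. State whether a rise at any of weeks 4, 8 and 12 counts, or only at week 12.
3. For the delayed-start within-group comparison, use the same number of baseline readings in each period (visits 2-3 for week 0, visits 6-7 for week 12), and state that this baseline differs from the between-group one.
4. Report the BP and medication components separately beside the composite.
5. Apply the same cut-offs to the mean of the period's last two visits (weeks 8 and 12; weeks 20 and 24) as a sensitivity analysis only, because it trades power for specificity.

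The cost is SAP wording. All readings are already scheduled, and no treatment rule changes. The one drawback is the second baseline definition, which must be explained in the report.
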